Interestingly, an intrinsically angiogenic impairment is also described in pregnancies complicated by congenital heart disease (CHD). (6) In particular, PIGF levels are found to be significantly lower and sFlt-1 levels significantly higher in the maternal plasma from pregnancies with fetuses with CHD in comparison to controls; so, women with pregnancies complicated by CHD show a similar circulation profile of women developing PE (6). This has been the scientific rationale for investigating the relationship between CHD and maternal increased risk of PE.–A Norwegian register-based study recently found associations between PE and CHD: in particular, early-PE is strongly associated with infant risk of CHD (7). Simultaneously, a Canadian population-based study found that overall PE was significantly associated with noncritical heart defects in offspring, whereas early-PE was associated with critical heart defects (8). Boyd H et al. in their study including 18,000 fetuses with CHD and 55,000 pregnancies with preeclampsia, have demonstrated that women carrying a fetus

with CHD, regardless of the type of defect, had a 7-fold increase in the risk of early-PE and 3-fold increase in the risk of late-preterm PE, whereas the association with term PE was weakly (9). Interestingly, women who had a previous child with CHD had a 2-fold greater risk of early PE and a 25% greater risk of term PE. Conversely early PE in a previously pregnancy was associated with a 6-fold increased risk of offspring CHD in the current pregnancy (10; 9). Moreover, placental histopathology examinations from pregnancies who underwent termination of pregnancy because of severe CHD showed that placental vascular malperfusion lesions were more common as compared with other fetal malformations (11).

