However, new interesting theories regarding the pathogenesis of PE have been recently highlighted: in particular, there is now emerging evidence that a suboptimal maternal cardiovascular performance resulting in uteroplacental hypoperfusion is more likely to be the first cause of placental dysfunction in preeclampsia. (12; 13) There are now several data from maternal echocardiography and angiogenic marker studies showing that cardiovascular dysfunction precedes the development of preeclampsia by several weeks or months (10). It is now well known that the cardiovascular system is markedly compromised in PE and plays a major role in the development of PE complications. Recent studies have elucidated the maternal hemodynamic profile associated with early-PE showing how this is typically associated to high maternal systemic vascular resistance (SVR) and low cardiac output (CO) (13). The recognition of the role of the cardiovascular etiology in PE has deep implications not only for the definition the pathophysiology of the disease but also for PE screening and diagnosis, clinical management, and therapy as recently the maternal hemodynamic assessment has entered in the clinical practice.

Although the similar pathogenic profile associated with PE and CHD and the well demonstrated data about the risk of PE in pregnancies complicated with CHD, to our knowledge, no investigations about maternal hemodynamic profile in these pregnancies has been previously proposed.

The aim of this study is to explore the maternal hemodynamic parameters detected by UltraSonic Cardiac Output Monitor (USCOM®) in women carrying a fetus with CHD and to eventually describe an association between those parameters and the presence of a fetal cardiac anomaly.

OBJECTIVES

Primary Objective: The aim of this study is to describe the maternal hemodynamic parameters detected by UltraSonic Cardiac Output Monitor (USCOM®) in women carrying a fetus with CHD and to possibly describe an association between those parameters and the presence of a fetal cardiac anomaly.

Secondary Objectives:

- To assess the number of cases of PE in our population of women carrying fetuses with CHD
- To assess the relationship between maternal hemodynamic profile and maternal and perinatal outcome
- To investigate associations between maternal hemodynamic parameters and the specific heart defect subtype

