- To explore the relationship between maternal hemodynamic parameters and fetal cardiac function and morphology in our population

METHODS

Study design This is a prospective monocentric interventional study with the use of the medical device UltraSonic Cardiac Output Monitor (USCOM®).

Study Population: Singleton pregnancy with a diagnosis of CHD performed at the Fetal Medicine Unit of Fondazione Policlinico A. Gemelli IRCCS during the study period and delivered at Fondazione Policlinico A. Gemelli IRCCS.

Study duration

The study has an expected duration of 36 months (three years). The study will begin when the ethics committee has issued a favorable opinion.

Inclusion criteria

The inclusion criteria are:

- Informed consent accepted
- Maternal Age >18 years
- Singleton pregnancy with a viable fetus at >20 weeks of gestation, with a diagnosis of CHD detected on antenatal ultrasound assessment and postnatally confirmed.

Exclusion criteria

The exclusion criteria are:

- Multiple pregnancy
- Pregnancy complicated by aneuploidy, genetic syndrome, or major structural fetal abnormality.
- Maternal congenital heart disease (GUCH)
- Maternal known cardiac disease

Variables and procedures

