Maternal hemodynamics assessment: Hemodynamic indices will be obtained using the USCOM® system. Women will undergo a hemodynamic investigation at the time of first diagnosis of CHD

during pregnancy or at the first assessment in Fondazione Policlinico A. Gemelli during pregnancy and then every two weeks until delivery. An additional hemodynamics evaluation will be performed in the post-partum period (in the 72 hours immediately after delivery). All hemodynamic assessment will be performed under standardized conditions. Maternal height, weight and brachial blood pressure will be obtained prior to hemodynamic assessment. USCOM® system utilizes continuous-wave Doppler, with a non-imaging probe in the suprasternal notch, to obtain velocity-time integrals of transaortic blood flow at the left ventricular outflow tract. Using an internal anthropometric algorithm, which correlates the outflow tract diameter with the patient's height, USCOM-1A multiplies the velocity-time integral by the aortic root diameter to calculate stroke volume. By measuring the time interval between each Doppler profile, heart rate (HR) can be calculated. CO (stroke volume \times HR) and SVR (MAP/CO) are calculated after inclusion of maternal mean arterial pressure. Participants remain in a semi recumbent position and a small amount of conducting gel is applied to their skin at the level of the suprasternal notch. The Doppler probe is applied and moved through three dimensions to ensure that the velocity of blood was being measured at the left ventricular outflow tract and not in the more distal aorta. Each Doppler acquisition used for analysis must register a minimum of two consecutive Doppler profiles (cardiac cycles). All hemodynamic measurements were performed by trained operators. USCOM-1A has been in clinical use since 2015. Its repeatability and reproducibility have been assessed in adult, pediatric and pregnant populations, demonstrating excellent agreement between operators with sufficient training (15; 16).

ENDPOINTS

Primary endpoint: To identify the maternal hemodynamic parametrics changes in pregnancies complicated by congenital heart diseases and immediately after delivery.

Secondary endpoints:

- prevalence of cases of preeclampsia in our population of pregnancies complicated by congenital heart disease
- To investigate association between maternal hemodynamic profile and perinatal outcome

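### The secondary preeclampsia endpoint is one crude prevalence with open-ended entry above 20 weeks and no listed date of preeclampsia diagnosis, so it hides the timing gradient in the protocol's own background

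*Protocol*

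**What the plan says.** **Endpoint.** Under ENDPOINTS, a secondary endpoint is the "prevalence of cases of preeclampsia in our population of pregnancies complicated by congenital heart disease". The matching item under OBJECTIVES is "To assess the number of cases of PE in our population of women carrying fetuses with CHD". Neither is divided by gestation. The PE definition under Variables and procedures (ISSHP 2018) has no early, late-preterm or term classes.

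**Background.** The text before OBJECTIVES reports that women carrying a fetus with CHD "had a 7-fold increase in the risk of early-PE and 3-fold increase in the risk of late-preterm PE", and only a weak association at term. It also cites a population-based study in which overall PE was linked to noncritical defects and early PE to critical ones. The pattern of high vascular resistance and low cardiac output is described for early PE.

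**Entry.** The inclusion criterion is "Singleton pregnancy with a viable fetus at >20 weeks of gestation, with a diagnosis of CHD detected on antenatal ultrasound assessment and postnatally confirmed". There is no upper gestational limit. Study Population describes a "Singleton pregnancy with a diagnosis of CHD performed at the Fetal Medicine Unit of Fondazione Policlinico A. Gemelli IRCCS during the study period", with delivery at the same centre. Maternal hemodynamics assessment places the first measurement at first CHD diagnosis "during pregnancy or at the first assessment in Fondazione Policlinico A. Gemelli during pregnancy and then every two weeks until delivery".

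**Data.** Variables and procedures lists gestational age at CHD diagnosis and at delivery, the incidence of hypertensive disorders, the presence of proteinuria, and maximum and minimum blood pressure and laboratory values. Gestational age at PE diagnosis is not listed.

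**The concern.** A proportion of women with PE has a clear meaning only if it is known over which part of pregnancy each woman was observed. Here that varies. A woman first seen at 35 weeks has, by construction, not already delivered elsewhere because of PE. She still counts in the denominator for the whole period after 20 weeks. A woman who already has PE at her first assessment counts as a case, with nothing to separate her from a woman who develops PE under follow-up. The first feature pulls the proportion down and the second can push it up. Both depend on referral timing rather than on PE risk in CHD pregnancies.

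In addition, the evidence the protocol cites is graded by timing, and a single pooled figure cannot show whether this cohort follows that gradient. At stake is whether a secondary descriptive result can be read against the protocol's own rationale. The hemodynamic primary endpoint is not affected.

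**Working it through.** The plan gives no expected PE rate, so there is no figure of its own to reproduce. The calculation below only illustrates size.

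**Inputs**
- From the protocol: n = 108; risk ratios of 7 (early) and 3 (late-preterm); a term association called weak, with no figure.
- Assumed: background risks of 0.5% early, 0.8% late-preterm and 2.5% term (total 3.8%); term ratio 1.0, varied to 1.2; a fraction f of women entering after the early window. The documents give neither background rates nor f.

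**1. Effect of pooling, everyone entering in time (f = 0)**
- Early: 7 × 0.5% = 3.5%, or 108 × 0.035 = 3.8 cases
- Late-preterm: 3 × 0.8% = 2.4%, or 2.6 cases
- Term: 1.0 × 2.5% = 2.5%, or 2.7 cases
- Pooled: 3.5 + 2.4 + 2.5 = 8.4%, or 9.1 cases
- Implied pooled ratio: 8.4 / 3.8 = 2.2

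With a term ratio of 1.2 the pooled ratio is 8.9 / 3.8 = 2.3. Over low (0.3 / 0.5 / 1.5%) to high (0.8 / 1.0 / 3.5%) backgrounds it stays between 2.2 and 2.4, and expected early cases run from 2.3 to 6.1. A 7-fold early excess therefore appears as roughly a doubling once classes are pooled.

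**2. Effect of late entry**

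Late entrants contribute no early PE. Their later risk is conditional on having had none:
- early(f) = (1 − f) × 3.5%
- pooled(f) = early(f) + 4.9% × [(1 − f) + f / (1 − 0.035)], where 4.9% = 2.4% + 2.5%

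| f | Early over all entrants | Apparent early ratio | Pooled |
|---|---|---|---|
| 0 | 3.5% | 7.0 | 8.4% |
| 25% | 2.6% | 5.25 | 2.63 + 4.94 = 7.6% |
| 50% | 1.75% | 3.5 | 1.75 + 4.99 = 6.7% |

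The early proportion falls by exactly the fraction f. The pooled prevalence falls much less: by about 10% of its value at f = 25% (7.6 / 8.4) and 20% at f = 50% (6.7 / 8.4).

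**3. What an entry-restricted denominator does**

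At f = 25%, 108 × 0.75 = 81 women are observed in the early window and 81 × 0.035 = 2.8 early cases are expected. At f = 50% the figures are 54 women and 1.9 cases. Both recover the 3.5% risk.

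**4. Precision (exact Clopper-Pearson 95% intervals)**
- Over 108 women: 2 cases = 1.9% (0.2 to 6.5%); 4 = 3.7% (1.0 to 9.2%); 6 = 5.6% (2.1 to 11.7%)
- With restricted denominators at the same 3.7%: 3/81 (0.8 to 10.4%); 2/54 (about 0.5 to 13%)

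**5. Eligibility wording**

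Study Population ties membership to a CHD diagnosis made at the unit. Maternal hemodynamics assessment names first assessment at the centre as an alternative to first diagnosis, which makes sense mainly for women diagnosed elsewhere. Which reading applies affects how many late referrals enter, and so affects f.

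**The case against.** **PE is secondary and descriptive.** This stands. The primary objective and endpoint are hemodynamic. A reader might infer that late entry dilutes the outcome on which the study is built; the documents do not support that.

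**The large relative loss belongs to a quantity the protocol does not name.** This also stands. No early-PE proportion is specified, there is no control group, and no comparison with registry rates is planned. A reader might infer that the stated endpoint is understated by the full late-entry share. On the illustration it moves only from 8.4% to 7.6% or 6.7%.

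**The background is not only about early PE.** Correct. It also cites overall and late-preterm PE, so a pooled count is legitimate and should stay.

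**Timing is partly recoverable.** Correct. Gestational age at delivery permits a proxy split, and brachial pressure taken before each two-weekly assessment roughly dates hypertension after entry. Neither dates the diagnosis of PE, which also needs proteinuria, organ dysfunction or growth restriction.

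**A separate SAP may define classes and denominators.** It may, and the variable list sits beside a general statement that pregnancy characteristics will be collected. But a SAP cannot supply a date the study did not record.

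**The assessment wording sets measurement timing, not eligibility.** This is a fair reading. It cannot be claimed that women diagnosed elsewhere are definitely admitted; the wording only leaves this open.

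**The net direction is unknown.** True. PE present at entry acts in the opposite direction, and the documents allow no estimate of its size.

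**Conclusion.** The point holds in a limited form. As written, the secondary PE prevalence combines classes that the protocol's background treats as differently associated with CHD. It does not separate PE present at entry from PE arising later, and it counts women who were not observed in the early window. Pooling is the larger effect on the stated endpoint: under the assumed backgrounds, a 7-fold early excess shows as a ratio of about 2.2 to 2.4. Late entry is the larger effect on any early-PE proportion, which falls by the late-entry share.

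These sizes rest on assumed background rates, an assumed term ratio of 1.0 to 1.2 and an assumed late-entry share. If most women enter near 20 to 24 weeks, the dilution is small. Nothing here undermines the primary analysis or makes the pooled count wrong as a count. The change is still worth making, because it is cheap and the missing date is best captured prospectively.

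**What to change.** 1. Keep the pooled PE figure.
2. Add gestational age at PE diagnosis to the list under Variables and procedures.
3. State the gestational cut-offs for early, late-preterm and term PE; the background text at hand uses these terms without giving limits.
4. Report each class with an exact interval among women enrolled before that class's upper limit, or as cumulative incidence on the gestational-age scale with delayed entry at first assessment.
5. Report PE already present at first assessment separately from PE arising afterwards.
6. Reconcile Study Population with Maternal hemodynamics assessment on whether women whose CHD was diagnosed elsewhere are eligible.

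The cost is one extra date per PE case and a few lines of endpoint wording. The downside is smaller denominators and wide intervals for a handful of early cases, about 2 to 6 under the assumptions above even if no woman enters late. The split should therefore be labelled descriptive.

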The following maternal hemodynamic indices will be evaluated: heart rate (HR) (beats per min; bpm), mean arterial pressure (mmHg), stroke volume (mL), cardiac output (CO) (L/min), systemic vascular resistance (dynes/s/cm⁵). Data on the demographic and pregnancy characteristics of participants, hemodynamic and ultrasound investigations, perinatal and delivery features will be also collected. In particular, the following variables will be included in the study: type of congenital heart defect, gestational age at diagnosis, fetal weight (EFW) and fetal weight centile at diagnosis of CHD and at the last scan before delivery, mean uterine arteries pulsatility index (UtA-PI), fetal umbilical artery (UA-PI) and middle cerebral artery pulsatility index (MCA-PI) at diagnosis and at the last scan before delivery, maternal age, height, pre-pregnancy weight and gestational weight gain, systolic and diastolic blood pressure values (maximum and minimum values), presence of proteinuria, biochemical maternal assessment (maximum and minimum values of creatinine and uric acid level, platelet count, liver enzyme level), incidence of hypertensive disorders of pregnancy, antihypertensive drug administration (type and dosage) including magnesium sulfate, antenatal steroid administration, mode of delivery and indications, gestational age at delivery, birthweight and birthweight centile, need of respiratory or cardiac support, neonatal intensive care unit admission and number of days, major neonatal complications, maternal morbidities (HELLP, eclampsia, intravascular disseminate coagulation, post-partum hemorrhage), and mortality. The following definitions of hypertensive disorders will be used, according to the International Society for the Study of Hypertension in Pregnancy (ISSHP) 2018 criteria (14): chronic hypertension (CH) will be defined as hypertension ($\geq 140/90$ mmHg) that predates pregnancy or is present prior to 20 weeks' gestation; gestational hypertension was defined as de-novo hypertension ($\geq 140/90$ mmHg) after 20 weeks' gestation; and preeclampsia (PE) will be defined as de-novo hypertension ($\geq 140/90$ mmHg) after 20 weeks' gestation with coexisting proteinuria, other maternal organ dysfunction or fetal growth restriction; preeclampsia superimposed to chronic hypertension (PE-CH).

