- To calculate correlation coefficients between the maternal hemodynamic parameters to the specific heart defect type
- To calculate correlation coefficients between the maternal hemodynamic parameters and fetal cardiac function and morphology parameters

STATISTICAL ANALYSIS PLAN

Sample size calculation

108 patients will be recruited

Statistical analysis

The sample will be described in its clinical and demographic characteristics by descriptive statistics techniques. In depth, qualitative data will be expressed as absolute and relative percentage frequency, whilst quantitative variables either by mean and standard deviation (SD) or median and interquartile range (IQR), as appropriate.

To verify the Gaussian distribution of quantitative variables, the Shapiro-Wilk test will be applied.

The discrete variables will be compared by Chi Square or Fisher Exact test.

Correlation analysis between hemodynamic parameters and variables related to the type of congenital heart defect of the fetus will be carried out by calculating and testing Pearson's and/or Spearman's correlation coefficient, when necessary Kendall's correlation coefficient will be used. Likewise, correlation analysis between hemodynamic parameters and fetal cardiac function parameters will be carried out.

To identify any differences in mean between baseline and immediate postpartum, continuous variables will be compared with the T test for paired data and/or the Wilcoxon test when appropriate.

Regression analysis will be performed to explore the relationship between maternal hemodynamic parameters and maternal and perinatal outcome and fetal cardiac parameters.

Mixed-effects models for longitudinal data will be fit to identify potential changes over time in maternal hemodynamic parameters also in relation to fetal cardiac parameters, controlling for any confounding variables.

All results will be considered statistically significant when $p < 0.05$.

All analyses will be conducted with R statistical software (R, cran, 2023).

Safety/Adverse Event Management

All adverse events observed during the study will be collected and recorded.

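### A secondary endpoint is defined as a correlation coefficient with type of heart defect, an unordered category; coded as one variable with three or more levels, the result depends on arbitrary codes

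*Protocol*

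**What the plan says.** The relevant text is in four places in the protocol.

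- **Endpoints, secondary endpoints.** One endpoint reads "To calculate correlation coefficients between the maternal hemodynamic parameters to the specific heart defect type". The endpoint is thus itself a coefficient, taken against defect type.
- **Statistical Analysis Plan, Statistical analysis.** The matching sentence plans "Correlation analysis between hemodynamic parameters and variables related to the type of congenital heart defect of the fetus", carried out by "calculating and testing Pearson's and/or Spearman's correlation coefficient, when necessary Kendall's correlation coefficient will be used".
- **Variables and procedures.** The data item is listed simply as type: "the following variables will be included in the study: type of congenital heart defect, gestational age at diagnosis". No order, severity score, grouping or numeric code is attached. The haemodynamic side (heart rate, mean arterial pressure, stroke volume, cardiac output, systemic vascular resistance) is continuous.
- **Objectives, secondary objectives.** The objective behind the endpoint is "To investigate associations between maternal hemodynamic parameters and the specific heart defect subtype". This is neutral wording and is not at fault.

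The other methods named do not reach this comparison. For categorical data: "The discrete variables will be compared by Chi Square or Fisher Exact test". The regression is to "explore the relationship between maternal hemodynamic parameters and maternal and perinatal outcome and fetal cardiac parameters". The mixed-effects models address change over time and fetal cardiac parameters. None names defect type.

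**The concern.** Pearson's coefficient needs a numeric scale. Spearman's and Kendall's need at least an order. Type of heart defect has neither. To compute any of the three on type as a single variable, someone must assign numbers to the defects, and with three or more types different assignments give different answers from the same data.

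Two things follow. A real difference between subtypes can be missed because the affected subtype received a middle code. And a positive or negative coefficient can be reported although its direction means nothing. Because no coding is fixed in advance and results are judged at p < 0.05, the coding could also be chosen after the data are seen.

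**Working it through.** The protocol gives no figure to reproduce here. It states 108 patients, without effect size, SD, power or number of defect types. Only n = 108 and the 0.05 level below come from the protocol. The number of types, the equal group sizes and the shifts are assumptions, and tests are taken as two-sided.

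**Step 1. Expected coefficient, six types.** Take six types of 18 women, coded 1 to 6. One type, with code c, has its mean raised by 1 SD.

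- Covariance of code and outcome: (c − 3.5)/6
- Variance of the codes: (6² − 1)/12 = 35/12 = 2.917
- Variance of the outcome: 1 + (1/6)(5/6) = 1.139
- r = [(c − 3.5)/6] / √(2.917 × 1.139) = [(c − 3.5)/6] / 1.823

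For c = 6: 0.4167/1.823 = +0.23. For c = 1: −0.23. For c = 4: 0.0833/1.823 = +0.05. The data are the same; only the label of the affected type has changed.

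**Step 2. Power in that scenario** (simulation, 4,000 runs per coding).

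| Code of affected type | 1 | 2 | 3 | 4 | 5 | 6 |
|---|---|---|---|---|---|---|
| Expected r | −0.23 | −0.14 | −0.05 | +0.05 | +0.14 | +0.23 |
| Pearson rejects at 0.05 | 0.68 | 0.29 | 0.06 | 0.06 | 0.27 | 0.69 |

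Repeat simulations put the top of the range at up to 0.71, hence about 70%. Spearman behaves the same way (about 0.07 to 0.67), so moving to ranks does not help.

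For the one-way F test the noncentrality is 108 × (1/6)(5/6) = 15 on 5 and 102 degrees of freedom, which gives power 0.84. Simulation gives 0.84 to 0.86. This does not depend on the labels.

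**Step 3. One data set, every possible coding.** For each number of types K, one data set of 108 was simulated and all assignments of integer codes were tried.

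| K (assumed means, SD units) | Pearson r | Pearson p | Codings with p < 0.05 | ANOVA p |
|---|---|---|---|---|
| 2 (0, 0.6) | −0.30 or +0.30 | 0.0015 under both | all | 0.0015 |
| 3 (0, 0.6, 0) | −0.24 to +0.24 | 0.014 to 0.51 | 33% | 0.041 |
| 4 (0, 0.6, 0, 0.6) | −0.33 to +0.33 | 0.0005 to 0.99 | 33% (8 of 24) | 0.0029 |
| 5 (0, 0.5, −0.5, 0.5, −0.3) | −0.41 to +0.41 | 0.00001 to 0.91 | 43% | 0.0005 |

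Spearman and Kendall show the same spread from K = 3 upwards. At K = 2 only the sign moves.

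**Step 4. The other coding.** In the six-type scenario, give each type its own 0/1 indicator. Pearson on the affected type's indicator rejects in about 97% of runs at 0.05, and in about 88% at 0.05/6. Swapping 0 and 1 changes only the sign. The fault therefore lies in putting three or more unordered types into one numeric variable, not in the coefficient as such.

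**The case against.** The strongest reply is that the analysis sentence speaks of variables related to the type of defect, not of type itself. That could mean 0/1 indicators, or a severity split such as the critical versus noncritical distinction that the background reports from a cited study. The coefficients are then legitimate, and Step 4 shows that indicators can perform well. The protocol nowhere says that types will be given integer codes, and coding is a detail that an analysis plan not shown here might settle.

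Much of this stands. A reader might infer that the protocol commits to an integer-coded correlation, or that its coefficients are invalid for this endpoint under any coding. The text supports neither. The 6% to 70% range describes one assumed coding and an assumed pattern of effects; it is not a property of the planned study.

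What does not stand is that nothing needs changing. The endpoint names the specific defect type, and no indicator, score or split is defined. A separate analysis plan that compared group means would have to depart from an endpoint defined as a coefficient. Nor can the planned regression on fetal cardiac parameters be assumed to cover defect type, since the protocol lists defect type and fetal cardiac function and morphology as separate secondary endpoints.

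A reader might also infer that this undermines the study. It does not: the primary endpoint, the paired baseline to postpartum comparison, the outcome regressions, the mixed models over time and the correlations with fetal cardiac function parameters are unaffected.

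**Conclusion.** The point holds in conditional form. The protocol defines a secondary endpoint by coefficients that do not suit an unordered category, and states no other analysis for it. If type enters as a single coded variable with three or more levels, size, sign and p-value depend on arbitrary codes, whatever the effect pattern. How far they move depends on the assumptions: with six equal subtypes, n = 108 and one subtype shifted by 1 SD, power is about 6% to 70% by coding, against about 84% for the F test. With two groups or 0/1 indicators only the sign is arbitrary.

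This is a should-fix: one of four secondary endpoints, in an exploratory single-centre study.

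**What to change.** Reword the endpoint as differences in maternal haemodynamic parameters between pre-defined defect groups. In the statistical analysis section, analyse defect group as a categorical factor, either by one-way ANOVA or Kruskal-Wallis or as a factor in the regression or mixed model already planned, and report group means with 95% confidence intervals. List the groups before analysis. Keep Pearson, Spearman and Kendall for continuous, ordinal or binary variables, including the fetal cardiac function parameters. The secondary objective on associations can stay as it is.

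The cost is one endpoint sentence, one analysis sentence and a grouping rule, with no new data or patients. The downside is that rare subtypes must be merged, so differences within a merged group will not be seen.

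### The maternal–fetal cardiac endpoint is a plain correlation across women measured at differing gestations, so a shared gestational trend can register as a significant link

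*Protocol*

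**What the plan says.** The Protocol's Secondary endpoints include: "To calculate correlation coefficients between the maternal hemodynamic parameters and fetal cardiac function and morphology parameters". The Statistical analysis section sets the method for defect type as "calculating and testing Pearson's and/or Spearman's correlation coefficient, when necessary Kendall's correlation coefficient will be used", and then extends it to the fetal measures: "Likewise, correlation analysis between hemodynamic parameters and fetal cardiac function parameters will be carried out". For this analysis it mentions no partial correlation, gestational-age term, gestation-standardised score or choice of visit. The decision rule covers the whole section: "All results will be considered statistically significant when" p is below 0.05.

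Gestation at measurement is left open. The Inclusion criteria ask for "Singleton pregnancy with a viable fetus at >20 weeks of gestation" and give no upper limit. Under Maternal hemodynamics assessment, "Women will undergo a hemodynamic investigation at the time of first diagnosis of CHD" or at her first assessment at the centre, with fortnightly readings after that up to delivery and one more after birth.

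The Statistical analysis section also plans two other analyses of this relationship. One is a regression involving fetal cardiac parameters, with no covariates named. The other is a set of mixed-effects models of maternal parameters over time, also in relation to fetal cardiac parameters, with control for unspecified confounders. Variables and procedures lists gestational age at diagnosis and at delivery. It does not list the fetal cardiac parameters or say whether they are raw or standardised.

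**The concern.** A simple correlation coefficient takes no covariates. If a maternal index and a fetal cardiac measure both drift with gestation, a woman measured late will tend to differ from a woman measured early on both. The coefficient then picks up the spread of gestations in the sample, even when the two measures are unrelated among women at the same gestation.

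The protocol allows for such drift on the maternal side, since it plans models to detect change over time. On the fetal side, cardiac dimensions grow with the fetus. The protocol collects fetal weight both as a value and as a centile, but states no equivalent standardisation for the fetal cardiac measures.

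At stake is the meaning of one secondary endpoint. Followed as written, the plan could report a shared gestational trend as an association between maternal hemodynamics and fetal cardiac function or morphology.

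**Working it through.** **Inputs from the Protocol.** Sample size: "108 patients will be recruited", given without effect size, SD, power or test, so it cannot be reproduced and is taken as it stands. Significance level: 0.05, sidedness not stated, taken as two-sided.

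**Assumed inputs.** The documents do not give the correlation of either measure with gestational age. Write a for the maternal index and b for the fetal measure, and let a run from 0 to 0.5 and b from 0.3 to 0.8. Each woman contributes one pair of values, and the effect of gestation is linear.

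**Step 1: the significance threshold.** With n = 108 there are 106 degrees of freedom and t = 1.983. The critical value is |r| = t / √(106 + t²) = 1.983 / √109.93 = 0.189.

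**Step 2: the correlation induced by gestation.** If the two measures are independent given gestational age, their marginal correlation is a × b. It reaches the threshold when a = b = √0.189, about 0.43. At that point about half of such studies would declare significance through gestation alone.

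**Step 3: the false-positive rate.** By Fisher's z, the rejection rate is approximately Φ(atanh(ab)·√105 − 1.96) plus the opposite tail. For (0.3, 0.8): ab = 0.24, atanh(0.24) = 0.2448, and 0.2448 × 10.247 = 2.508. Then 2.508 − 1.96 = 0.548 and Φ(0.548) = 0.708. A simulation of 40,000 data sets per scenario gives 71.1%, in agreement.

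| Assumed (a, b) | Induced r = ab | Plain Pearson test | Partial correlation given gestational age |
|---|---|---|---|
| (0, 0.8) | 0 | 4.9% | 5.1% |
| (0.1, 0.5) | 0.05 | 8.1% | 5.0% |
| (0.3, 0.3) | 0.09 | 15.3% | 5.1% |
| (0.2, 0.5) | 0.10 | 17.9% | 4.9% |
| (0.2, 0.8) | 0.16 | 37.8% | 4.9% |
| (0.3, 0.6) | 0.18 | 46.6% | 4.9% |
| (0.3, 0.8) | 0.24 | 71.1% | 5.1% |
| (0.5, 0.8) | 0.40 | 99.2% | 5.2% |

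The figures are for Pearson's coefficient. Spearman and Kendall do not condition on gestation either, so the mechanism carries over, but rates for them were not computed. Gestation-standardised fetal measures would set b near 0, which makes ab near 0 and leaves the plain test at about 5%.

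**The case against.** The strongest reply is that the same section already plans a regression and a confounder-controlled mixed model on this relationship, and that a covariate list may properly sit in a separate analysis plan that is not shown. That stands in part: the correlation is not the only analysis, and unnamed covariates alone would not be a finding. But the protocol fixes the correlation coefficient as the endpoint and names the tests for it. Neither model is tied to that endpoint, and nothing says which result prevails if they disagree.

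A second reply also stands: the fetal parameters are not listed, and coefficients computed on gestational-age z-scores would fit the endpoint wording and remove the problem. The text neither requires nor excludes this.

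Three stronger readings are tempting and are not supported.

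- A reader might infer that gestation is bound to create significant correlations. The documents give no correlation of either measure with gestation, and the inflation is nil or modest when the dependence is absent or weak. Nor do they say that the maternal and fetal readings of one woman are taken at different gestations; the variation shown is between women.
- A reader might infer that the fortnightly readings will be pooled as if independent. The protocol does not state this, and it names mixed models for the longitudinal data.
- The device is described as "Using an internal anthropometric algorithm, which correlates the outflow tract diameter with the patient's height", and a reader might infer that body size biases these correlations. That would need the fetal cardiac measures to depend on maternal height as well, which the documents do not show.

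**Conclusion.** The point holds in conditional form. The endpoint statistic is an unadjusted coefficient in women whose gestation at measurement is not controlled, so a gestational trend shared by both measures can appear as a maternal–fetal association. Across the assumed range the false-positive rate runs from about 5% to 99%, with 18% to 71% for the middle cases from (0.2, 0.5) to (0.3, 0.8). It stays at 4.9% to 5.2% once gestational age is partialled out. These figures rest on the assumed correlations, one pair of values per woman, a linear gestational effect and a two-sided test. The point concerns one secondary endpoint; the primary endpoint does not depend on these coefficients. It should be corrected because the bias may be large and the remedy is nearly free.

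**What to change.** Redefine this secondary endpoint as a gestation-adjusted association, reported with a 95% confidence interval. Either of two routes would do:

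- At one specified visit per woman, use the partial correlation given gestational age at the reading, or express the fetal measures as gestational-age z-scores before correlating them.
- Make the already planned mixed model the analysis of this endpoint, with gestational age named as a covariate and a random intercept per woman.

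State which fetal cardiac parameters are analysed and whether they are raw or standardised. If the relation with gestation is not linear, the adjustment should allow for that.

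The cost is a change of wording and a little data handling. The protocol lists gestational age at diagnosis and at delivery, not at each assessment, so gestation at each reading has to be derived from visit dates. No extra women or procedures are needed.
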